[Part 3 of 3 of the document. The other parts are not shown.]

- Results in death
- Is life threatening; this means that the patient was at risk of death at the time of the event; it does not mean that the event hypothetically might have caused death if it were more severe
- Requires hospitalization or prolongation in existing hospitalization
- Results in persistent or significant incapacity or substantial disruption of the ability to conduct normal life functions
- Is a congenital anomaly or birth defect
- Is another important medical event (see below)

Important medical events that do not result in death, are not life threatening, or do not require hospitalization may be considered SAEs when, based on appropriate medical judgment, they may jeopardize the patient and may require medical or surgical intervention to prevent 1 of the outcomes listed in this definition. Examples of such events are:

-
- Intensive treatment in an emergency room or at home for allergic bronchospasm
 - Blood dyscrasias or convulsions that do not result in inpatient hospitalization
 - Development of drug dependency or drug abuse

Hospitalization for elective surgery or routine clinical procedures that are not the result of AE (eg, elective surgery for a pre-existing condition that has not worsened) need not be considered SAEs. If anything untoward is reported during the procedure, that occurrence must be reported as an AE, either 'serious' or 'nonserious' according to the usual criteria.

Suspected unexpected serious adverse reactions (SUSARs) are AEs that are associated with the use of the drug and are serious and unexpected.

6.2.2.6 Adverse Events of Special Interest

AEs of special interest in this study include the following:

1. Anaphylaxis and serious allergic reactions
2. Grades 2 to 5 injection site reaction, including erythema, pain, and induration (See [APPENDIX 6](#))
3. Drug Induced Liver Injury (DILI) assessed following Hy's Law
4. Malignancy
5. Opportunistic infections such as disseminated histoplasmosis, cryptococcosis, and disseminated tuberculosis
6. Cryptosporidiasis

6.2.2.6.1 Anaphylaxis and Serious Allergic Reactions

Anaphylaxis will be defined according to the National Institute of Allergy and Infectious Diseases/Food Allergy and Anaphylaxis Network (NIAID/FAAN) criteria.⁴² In the event of anaphylactic reaction or severe/serious hypersensitivity/allergic reaction, the patient must discontinue IP and emergency resuscitation measures implemented. In case of other mild to moderate hypersensitivity reaction, depending on the severity, the investigator may manage in accordance with the standard-of-care.

Anaphylaxis is highly likely when any one of the following 3 criteria is fulfilled:

1. Acute onset of an illness (minutes to several hours) with involvement of the skin, mucosal tissue, or both (eg, generalized hives, pruritus, or flushing, swollen lips-tongue-uvula) and at least 1 of the following:
 - a. Respiratory compromise (eg, dyspnea, wheeze-bronchospasm, stridor, reduced peak expiratory flow [PEF], hypoxemia)
 - b. Reduced blood pressure or associated symptoms of end-organ dysfunction (eg, hypotonia [collapse], syncope, incontinence)

2. Two or more of the following that occur rapidly after exposure to a likely allergen for that patient (minutes to several hours):
 - a. Involvement of the skin-mucosal tissue (eg, generalized hives, itch-flush, swollen lips-tongue-uvula)
 - b. Respiratory compromise (eg, dyspnea, wheeze-bronchospasm, stridor, reduced PEF, hypoxemia)
 - c. Reduced blood pressure or associated symptoms (eg, hypotonia [collapse], syncope, incontinence)
 - d. Persistent gastrointestinal symptoms (eg, crampy abdominal pain, vomiting)
3. Reduced blood pressure after exposure to known allergen for that patient (minutes to several hours):
 - a. Systolic blood pressure of less than 90 mm Hg or greater than 30% decrease from the patient's baseline

6.2.2.6.2 *Injection Site Reactions*

Injection site reactions are to be captured and reported as AEs. These will include Grades 2 to 5 injection site erythema, pain, and induration (see [APPENDIX 6](#)). The investigator should provide a clear description of the observed or reported AE including location and severity. All concomitant treatments used to treat injection site reactions should be recorded and captured in the eCRF, together with the AE of injection site reactions.

6.2.2.6.3 *Potential Drug-Induced Liver Injury*

Abnormal values in AST and/or ALT levels concurrent with abnormal elevations in total bilirubin level that meet the criteria outlined below in the absence of other causes of liver injury are considered potential cases of DILI, and as potential Hy's Law cases, and should always be considered important medical events. If symptoms compatible with DILI precede knowledge of serum chemical test abnormalities, liver enzyme measurements should be made immediately, regardless of when the next visit or monitoring interval is scheduled. In some cases, symptoms may be an early sign of injury and although typically less sensitive than serum enzyme elevations, they may indicate a need for prompt serum testing. An increase in liver enzymes should be confirmed by a repeated test within 48 to 72 hours following the initial test, prior to reporting of a potential DILI event. Patients will continue to have weekly or biweekly liver enzyme measurements until resolution or levels return to baseline.

All occurrences of potential DILIs, meeting the defined criteria, must be reported as SAEs (see [Section 6.2.2.7.2](#) for reporting details).

Potential DILI is defined as:

1. ALT or AST elevation $> 3 \times$ ULN

AND

2. Total bilirubin $> 2 \times$ ULN, without initial findings of cholestasis (elevated serum alkaline phosphatase)

AND

3. No other immediately apparent possible causes of ALT or AST elevation and hyperbilirubinemia, including, but not limited to, viral hepatitis, pre-existing chronic or acute liver disease, or the administration of other drug(s) known to be hepatotoxic

The patient should return to the investigational site and be evaluated as soon as possible, include laboratory tests, detailed history, and physical assessment. In addition to repeating measurements of AST and ALT, laboratory tests should include albumin, CK, total bilirubin, direct and indirect bilirubin, GGT, prothrombin time (PT)/International Normalized Ratio (INR), and alkaline phosphatase. A detailed history, including relevant information, such as review of ethanol, acetaminophen, recreational drug and supplement consumption, family history, occupational exposure, sexual history, travel history, history of contact with a jaundiced person, surgery, blood transfusion, history of liver or allergic disease, and work exposure, should be collected. Further testing for acute hepatitis A, B, or C infection and liver imaging (eg, biliary tract) may be warranted. All cases confirmed on repeat testing as meeting the laboratory criteria defined above, with no other cause for liver function test (LFT) abnormalities identified at the time should be considered potential Hy's Law cases irrespective of availability of all the results of the investigations performed to determine etiology of the abnormal LFTs. Such potential Hy's Law cases should be reported as SAEs.

Study drug discontinuation is considered if there is marked serum AST or ALT elevation or evidence of functional impairment (as indicated by rising bilirubin or INR, which represent substantial liver injury) that is related to study drug. Discontinuation of treatment should be considered if:

- ALT or AST $> 8 \times$ ULN
- ALT or AST $> 5 \times$ ULN for more than 2 weeks

Discontinuation of treatment must occur if:

- ALT or AST $> 3 \times$ ULN and (total bilirubin $> 2 \times$ ULN or INR > 1.5)
- ALT or AST $> 3 \times$ ULN with the appearance of fatigue, nausea, vomiting, right upper quadrant pain or tenderness, fever, rash, and/or eosinophilia ($> 5\%$)

6.2.2.6.4 Malignancy

The identification of a malignancy event will be made by the study site and communicated to the sponsor or designee. AEs should be reported as serious per the criteria in [Section 6.2.2.5](#).

After the first dose of study drug, when there is a decision to biopsy a potentially malignant tumor, lymph node, or other tissue, the investigator and/or consultant(s) should contact the sponsor clinicians or designee to discuss the issue and any decisions as soon as possible.

6.2.2.6.5 *Specific Infections*

Any diagnosis or suggested diagnosis of opportunistic infections such as disseminated histoplasmosis, cryptococcosis, shingles, disseminated herpes simplex, or disseminated tuberculosis will be recorded as AEs of special interest.

Cryptosporidiosis is also considered an AE of special interest. Patients will be evaluated for cryptosporidium in the stool at screening, and as clinically indicated (eg, watery diarrhea) during the study. If a patient develops diarrhea during the study a stool sample must be provided to test for ova, parasites, and cryptosporidium.

6.2.2.7 Reporting of Adverse Events

AE reporting will be carried out in accordance with applicable local regulations, including regulatory agency and IRB reporting requirements.

Each AE is to be assessed to determine if it meets the criteria for an SAE. If an SAE occurs, expedited reporting will follow local and international regulations, as appropriate, and is further outlined in [Section 6.2.2.7.2](#).

6.2.2.7.1 Reporting of Pregnancy

As information is available, a pregnancy diagnosed during the study will be reported within 24 hours to the sponsor via the Pregnancy Notification and Outcome Form, including pregnancy in female patients who received study drug and female partners of male study patients who received study drug. The pregnancy should be followed to term and/or outcome and this outcome should also be reported to the sponsor via the Pregnancy Notification and Outcome Form. Pregnancy itself is not regarded as an AE or SAE unless there is complication.

In the case of a live birth, the structural integrity of the neonate can be assessed at the time of birth. In the event of a termination, the reason(s) for termination should be specified and, if clinically possible, the structural integrity of the terminated fetus should be assessed by gross visual inspection (unless pre-procedure test findings are conclusive for a congenital anomaly and the findings are reported).

If the outcome of the pregnancy meets the criteria for an AE or SAE (ie, ectopic pregnancy, spontaneous abortion, intrauterine fetal demise, neonatal death, or congenital anomaly [in a live born, a terminated fetus, an intrauterine fetal demise, or a neonatal death]), the investigator should follow the procedures for reporting SAEs.

Additional information about pregnancy outcomes that are reported as SAEs follows:

- Spontaneous abortion includes miscarriage and missed abortion
- Neonatal deaths that occur within 1 month of birth should be reported, without regard to causality, as SAEs. In addition, infant deaths after 1 month should be reported as serious adverse events when the investigator assesses the neonatal death as related or possibly related to exposure to investigational product.

6.2.2.7.2 *Reporting of Serious Adverse Events*

The principal investigator is responsible for providing notification to the sponsor of any SAE via the Safety Adverse Event Form, whether deemed study drug related or not, that a patient experiences during their participation in this study within 24 hours of becoming aware of the event.

If an SAE is fatal or life threatening, notification to the sponsor must be made aware immediately, irrespective of the extent of available AE information. This timeframe also applies to additional new information (follow-up) on previously forwarded SAE reports as well as to the initial and follow-up reporting of exposure during pregnancy and exposure via breastfeeding cases. In the rare event that the investigator does not become aware of the occurrence of an SAE immediately (eg, if an outpatient study patient initially seeks treatment elsewhere), the investigator is to report the event within 24 hours after learning of it and document the time of his/her first awareness of the AE.

The principal investigator will review each SAE and evaluate the intensity and the causal relationship of the event to the study drug. All SAEs will be recorded from the time of first dose of study drug through the safety follow-up period (up to Day 270). SAEs occurring after the final follow-up visit and coming to the attention of the principal investigator must be reported only if there is (in the opinion of the principal investigator) reasonable causal relationship with the study drug.

As a minimum requirement, the initial notification should provide the following information:

- Study number
- Patient number
- Details of the SAE (verbatim details are sufficient for immediate notification)
- Criterion for classification as ‘serious’
- Causality assessment (which may be updated in a follow-up report when sufficient information is available to make this classification)

Initial reports of SAEs must be followed later with detailed descriptions, including clear photocopies of other documents as necessary (eg, hospital reports, consultant reports, autopsy reports, etc), with the study patient’s personal identifiers removed. All relevant information obtained by the principal investigator through review of these documents will be recorded and submitted to the sponsor within 24 hours of receipt of the information. If a new Safety Adverse Event Form is submitted, then the principal investigator must sign and date the form. The sponsor may also request additional information on the SAE, or clarification of omitted or discrepant information from the initial notification, which the principal investigator or an authorized delegate should submit to the sponsor within 24 hours of the request as possible.

6.2.2.7.3 *Reporting of Adverse Events of Special Interest*

AEs of special interest will be reported to safety immediately or within 24 hours of the site becomes aware of the event and recorded as such on the Adverse Events eCRF and Safety Adverse Event Form.

Potential DILI will be reported based on specifications mentioned in [Section 6.2.2.6.3](#).

Each AE of special interest is to be assessed to determine if it meets the criteria for an SAE. If an SAE occurs, expedited reporting will follow local and international regulations, as appropriate, and is further outlined in [Section 6.2.2.7.2](#).

6.2.2.8 Follow Up of Adverse Events

All AEs will be followed up through the safety follow-up visits. All SAEs experienced by a patient, irrespective of the suspected causality, will be monitored until the event has resolved, until any abnormal laboratory values have returned to baseline or stabilized at a level acceptable to the principal investigator and medical monitor, until there is a satisfactory explanation for the changes observed, or until the patient is lost to follow-up.

See [Section 6.2.2.7.1](#) for details related to follow-up of pregnancy. See [Section 6.2.2.6.3](#) for details related to follow-up of potential DILI. See [Section 6.2.2.6.4](#) for details related to follow-up of malignancy.

6.2.3 Vital Signs

Vital signs (blood pressure, heart rate, and body temperature) will be assessed as specified in the Schedule of Assessments ([Section 3.4](#)). Vital signs will be assessed on Day 0 at predose and at 1 and 2 hours postdose, as well as on each of the scheduled visit days during the study (excluding PK-only site visits). Supine BP and heart rate recordings will be made after the patient has been recumbent and at rest ≥ 5 minutes. When the timing of these measurements coincides with a blood collection, vital signs should be obtained prior to the time of the blood collection.

6.2.4 12-Lead Electrocardiograms

ECG will be assessed as specified in the Schedule of Assessments ([Section 3.4](#)). ECG recording will initiate after the patient has been supine for at least 5 minutes. On days of PK blood draws, the ECG will be collected before scheduled PK blood draws, though timing will be such that PK draws are collected on their scheduled times where possible.

The ECG will include all 12 standard leads and a Lead II rhythm strip on the bottom of the tracing. The ECG will be recorded at a paper speed of 25 mm/second. The following ECG parameters will be collected: PR interval, QRS interval, RR interval, QT interval, and QT interval corrected for heart rate using Fridericia's formula (QTcF).

All ECGs must be evaluated by a qualified physician or qualified designee for the presence of abnormalities and will be captured electronically and retained for future evaluation if required, up to the time of the clinical study report (CSR) completion.

6.2.5 Physical Examinations

The full physical examination will be completed at screening and Day 0. It includes an assessment of general appearance and evaluation of head, eyes, ears, nose, mouth, throat, neck,

thyroid, lymph nodes, and extremities, and dermatologic, respiratory, cardiovascular, gastrointestinal, musculoskeletal, neurologic, and psychiatric systems.

The targeted (limited) physical examination will be completed at all other visits as indicated in the Schedule of Assessments ([Section 3.4](#)). It includes evaluation of patient complaints and SLE disease-related issues, and will exclude the genitourinary system.

6.2.6 C-SSRS

The C-SSRS is a low-burden measure of the spectrum of suicidal ideation and behavior that was developed by Columbia University researchers for the National Institute of Mental Health Treatment of Adolescent Suicide Attempters Study to assess severity and track suicidal events through any treatment. It is a clinical interview providing a summary of both ideation and behavior that can be administered during any evaluation or risk assessment to identify the level and type of suicidality present. The C-SSRS can also be used during treatment to monitor for clinical worsening.⁴³

The C-SSRS evaluation will be performed as specified in the Schedule of Assessments (Section 3.4). Patients with recent (within the past 12 months) or active suicidal ideation or behavior based on patient responding “yes” to question 3, 4, or 5 is exclusionary at screening will be excluded from the study. Patients with recent or active suicidal ideation or behavior at subsequent study visits will have responses to the C-SSRS reviewed in detail to assess patient risk, and appropriate consultative mental health services will be provided.

6.2.7 Injection Site Reactions

Patients will be monitored for local injection site reactions as specified in the Schedule of Assessments (Section 3.4). Local injection site reactions will be assessed at 2 hours postdose at baseline, and predose for each injection after baseline. Injection site reactions should be managed according to the standard of care. Injection site reactions, Grades 2 to 5, are to be reported as AEs of special interest (see [Section 6.2.2.7.3](#)).

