	
Safety
 
 • To assess safety and tolerability of repeat doses of BOS161721 (20, 60, and 120 mg) administered SC in adult patients with moderately to severely active SLE on limited background standard of care treatment 	
Safety Endpoints
 
 • Incidence and severity of adverse events (AEs) and serious adverse events (SAEs), related AEs, AEs leading to study drug discontinuation, AEs by severity and relatedness • Injection site reactions • C-SSRS • 12-lead ECGs parameter results at each visit and change from baseline • Vital signs (blood

Section	Description of Changes	Rationale
		pressure [BP], heart rate, and temperature) parameter results at each visit and change from baseline 
 • Clinical laboratory results and change from baseline • Physical examinations changes from baseline • ADAs • Study drug exposure/compliance • Concomitant medication usage
	Exploratory	

 • CCI [REDACTED] 	
 • CCI [REDACTED] 	
 • CCI [REDACTED]

 • CCI [REDACTED] 	
 • CCI [REDACTED] 	
 • CCI [REDACTED]

 • CCI [REDACTED] 	
 • CCI [REDACTED] 	
 • CCI [REDACTED]

Section	Description of Changes	Rationale
PROTOCOL SUMMARY , Study Design	Replace: The trial will consist of a staggered MAD Phase 1b and POC Phase 2 studies. Both studies will be double blinded with each patient having the same number of doses (7), and visits; the duration will be 180 days, followed by a 90-day follow-up safety observation period. With: The trial will consist of 2 double-blinded studies : MAD Phase 1b and POC Phase 2. Patients may receive a total of 7 SC monthly doses of study drug on Days 0, 30, 60, 90, 120, 150, and 180, followed by safety follow-up visits at Days 210, 240, and 270.	Clarification that patients will not have the same number of visits in both studies.

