Section 5.1.1, Retesting During Screening Period	Add: 
there is evidence a laboratory sample was mislabeled, indeterminate, inadequately processed, and/or deteriorated in transit to the central laboratory	Text added for further clarification
Section 5.2, Enrollment/Randomization and Day 0 Treatment	Replace: 
pSTAT3 (predose [trough] samples only in Phase 2) With: 
pSTAT3 (predose [trough] samples only in Phase 1b)	Updated to clarify the planned laboratory assessments
Section 5.2, Enrollment/Randomization and Day 0 Treatment	Delete: 
CCI	Updated to clarify the planned laboratory assessments
Section 5.3, Treatment Period/Follow-Up Visits		
Section 5.2, Enrollment/Randomization and Day 0 Treatment	Replace: 
Injection site reaction assessment, predose, and 2 hours post dose	Clarified that no need for predose injection site

Section	Description of Changes	Rationale		
0 Treatment	With: Injection site reaction assessment, performed at 2 hours postdose	reaction assessment at baseline		
Section 5.3 , Treatment Period/Follow-Up Visits	Delete: 
 Injection site reaction assessments will be performed predose and 2 hours postdose 	Clarified that no need for predose injection site reaction assessment at baseline		
Section 5.3 , Treatment Period/Follow-Up Visits	Add: 
 pSTAT3 (predose [trough] samples only Phase 1b) 	Updated to clarify the planned laboratory assessments		
Section 5.4 , Safety Follow-Up Visits	Delete: 
 pSTAT3 	Updated to clarify the planned laboratory assessments		
Section 6.6 , Pharmacodynamic Assessments				
Section 5.4 , Safety Follow-Up Visits	Delete: 
 pSTAT3 	Updated to clarify the planned laboratory assessments		
Section 6.2.1 , Laboratory Assessments (Table 3)	Delete: 
 
 Hematology	
 
 Reticulocytes (%)	
 
	Hematology	Reticulocytes (%)	Updated to clarify the planned laboratory assessments
Hematology				
Reticulocytes (%)				

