Section 6.2.1 , Laboratory Assessments (Table 3)	Replace: 
 
 Immunogenicity, PD and other Biomarker Tests	
 
 pSTAT3 (predose [trough] samples only, in Phase 2)	
 
	Immunogenicity, PD and other Biomarker Tests	pSTAT3 (predose [trough] samples only, in Phase 2)	Updated to clarify the planned laboratory assessments
Immunogenicity, PD and other Biomarker Tests				
pSTAT3 (predose [trough] samples only, in Phase 2)				
Section 6.2.1 , Laboratory Assessments (Table 3 footnotes)	With: 
 
 Immunogenicity, PD and other Biomarker Tests	
 
 pSTAT3 (predose [trough] samples only in Phase 1b)	
 
	Immunogenicity, PD and other Biomarker Tests	pSTAT3 (predose [trough] samples only in Phase 1b)	
Immunogenicity, PD and other Biomarker Tests				
pSTAT3 (predose [trough] samples only in Phase 1b)				
Section 6.2.1 , Laboratory Assessments (Table 3 footnotes)	Add: h If clinically indicated for hemolytic anemia .	Text updated to clarify when Coomb's test direct will be collected		

Section	Description of Changes	Rationale
Section 6.2.2.6, Adverse Events of Special Interest	Replace: 2 Injection site reaction, including erythema, pain, and induration With: 2 Grades 2 to 5 injection site reaction, including erythema, pain, and induration (See APPENDIX 6)	Clarify that Grades 2 to 5 injection site reactions are AEs of special interest
Section 6.2.2.6.2, Injection Site Reactions	Replace: These may include injection site erythema, pain, and induration. With: These will include Grades 2 to 5 injection site erythema, pain, and induration (see APPENDIX 6).	Clarify that Grades 2 to 5 injection site reactions are AEs of special interest
Section 6.2.7, Injection Site Reaction	Replace: Local injection site reactions will be assessed predose and at 2 hours postdose. Injection site reactions should be managed according to the standard of care. Injection site reactions are to be reported as AEs of special interest (see Section 6.2.2.7.3). With: Local injection site reactions will be assessed at 2 hours postdose at baseline, and predose for each injection after baseline . Injection site reactions should be managed according to the standard of care. Injection site reactions, Grades 2 to 5 , are to be reported as AEs of special interest (see Section 6.2.2.7.3).	Clarify that Grades 2 to 5 injection site reactions are AEs of special interest

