- ^p Postdose samples will be collected at 4, 8, and 24 hours after study drug administration on Days 0, 30, and 180.

Table 2. Schedule of Assessments - Phase 2 Proof of Concept (POC) Study

	Screen ^a	Enroll	Treatment Period Follow-up									Safety Follow-Up		
Days	-28 to -1	0	15 (± 3)	30 (± 3)	60 (± 3)	90 (± 3)	120 (± 3)	150 (± 3)	180 (± 3)	187 (± 3)	195 (± 3)	210 (± 3)	240 (± 3)	270 (± 3)
Visit Number	1	2	3	4	5	6	7	8	9	--	--	10	11	12
GENERAL ASSESSMENTS														
Informed consent	X													
Inclusion/Exclusion criteria	X													
Medical history	X													
Demographics	X													
SLICC Criteria for SLE	X													
Concomitant medication ^b	X	X	X	X	X	X	X	X	X	X	X	X	X	X
Randomization ^c		X												
BOS161721 or placebo dosing		X		X	X	X	X	X	X					
SAFETY ASSESSMENTS														
Full physical exam	X	X												
Chest x-ray ^d	X													
C-SSRS	X	X				X			X					
AEs and SAEs		X	X	X	X	X	X	X	X	X	X	X	X	X
12-lead ECG ^e	X	X		X		X								X
Injection site reaction assessment ^f		X		X	X	X	X	X	X	X	X	X	X	X
Targeted physical examination			X	X	X	X	X	X	X			X	X	X
Vital signs (BP, HR, and temperature) ^g	X	X	X	X	X	X	X	X	X			X	X	X
EFFICACY ASSESSMENTS														
BILAG-2004 Index	X	X		X	X	X	X	X	X			X	X	X
SLEDAI-2K	X	X		X	X	X	X	X	X			X	X	X
PGA	X	X		X	X	X	X	X	X			X	X	X
ACR-28 joint count	X	X		X	X	X	X	X	X			X	X	X
CLASI	X	X		X	X	X	X	X	X			X	X	X
CCI		X		X	X	X	X	X	X			X	X	X

Table 2. Schedule of Assessments - Phase 2 Proof of Concept (POC) Study

Days	Screen ^a	Enroll	Treatment Period Follow-up									Safety Follow-Up		
	-28 to -1	0	15 (± 3)	30 (± 3)	60 (± 3)	90 (± 3)	120 (± 3)	150 (± 3)	180 (± 3)	187 (± 3)	195 (± 3)	210 (± 3)	240 (± 3)	270 (± 3)
Visit Number	1	2	3	4	5	6	7	8	9	--	--	10	11	12
SLICC/ACR Damage Index		X							X					
CCI		X		X	X	X	X	X	X			X	X	X
LABORATORY ASSESSMENTS														
CD4+ count	X	X	X	X		X			X					
Clinical laboratory assessments (hematology and clinical chemistry) ^h	X	X		X	X	X	X	X	X			X	X	X
Coomb's test direct ⁱ	X	X		X	X	X	X	X	X			X	X	X
Total IgG and IgM	X	X	X	X		X			X					
Plasma CCI	X	X		X	X	X	X	X	X			X	X	X
Plasma CCI & CCI	X	X	X	X	X	X			X					
Whole blood for leukocyte immunophenotype	X	X	X	X	X	X			X					
ADA ^j		X	X	X	X	X			X					X
nAb ^k						X			X					
pSTAT3 ^l		X		X	X	X			X					
CCI		X							X					
Whole blood RNA collection		X	X	X		X								X
CCI	X	X		X	X	X	X	X	X			X ^m	X ^m	X ^m
CRP	X					X								X
Serum pregnancy test (women)	X													
FSH (postmenopausal women)	X													

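### Section 6.2.7 keeps the 2-hour postdose injection-site check for only the first of 7 injections, so ascertainment after repeat doses rests on later predose checks, follow-up visits and reported events

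*Protocol*

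**What the plan says.** Section 6.2.7 of V3.0 sets the timing: "Local injection site reactions will be assessed at 2 hours postdose at baseline, and predose for each injection after baseline". It also gives the event its status: "Injection site reactions, Grades 2 to 5, are to be reported as AEs of special interest". The section defers to the Schedule of Assessments (Section 3.4) for visit days.

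The dosing plan, in the new wording recorded in Appendix 7 for the study design, is: "Patients may receive a total of 7 SC monthly doses of study drug on Days 0, 30, 60, 90, 120, 150, and 180".

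Appendix 7 shows what Section 6.2.7 said before: "Local injection site reactions will be assessed predose and at 2 hours postdose". It also lists, under deletions from Section 5.3 (treatment-period visits), the line: "Injection site reaction assessments will be performed predose and 2 hours postdose". Its excerpts of the revised schedule tables move the footnote that specifies 2 hours postdose from the row label to the Day 0 cell. The reason given for the Section 5.2, 5.3 and footnote edits is: "Clarified that no need for predose injection site reaction assessment at baseline". The reason given for the Section 6.2.7 row is the restriction to Grades 2 to 5. The table rows carry only a general remark about clarifying when assessments are collected.

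For Phase 1b PK sampling, the V2.0 schedule (Section 4.3, Table 1, footnote p) reads: "Postdose samples will be collected at 4, 8, and 24 hours after study drug administration on Days 0, 30, and 180". Appendix 7 logs no change to it.

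**The concern.** A predose check on a dosing day cannot show the reaction to the injection about to be given; it can only look back at the previous one. Under the current wording, the acute reaction is therefore looked for on schedule after dose 1 and after no later dose.

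Injection-site reactions are a listed safety endpoint in both phases, and a primary safety endpoint in Phase 1b. Grading under Appendix 6 relies partly on inspection: erythema is graded by body surface area, and edema, phlebitis and ulceration are distinguished from tenderness. A patient's account a month later is a weaker basis for a grade than an examination.

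What is at stake is the repeat-dose picture. If dose 1 is examined at 2 hours and later doses are not, a change in incidence or grade across injections mixes any true change with a change in how reactions are found. The edit also looks unintended, because none of the stated reasons concerns postdose checks after later injections.

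**Working it through.** The protocol states no figure on this point, so there is nothing to reproduce. The check is a count over the dosing days.

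Inputs:
- Dosing days 0, 30, 60, 90, 120, 150 and 180 (Appendix 7, study design).
- Current timing rule: 2 hours postdose at baseline, predose afterwards (Section 6.2.7).
- Superseded rule: predose and 2 hours postdose (Appendix 7; V2.0 Section 7.2.7).
- Other days with a site assessment: Day 7 (Phase 1b only), 187, 195, 210, 240 and 270, from the V2.0 schedule tables, because the current Section 3.4 is not in the part of the protocol at hand. Visit windows are ±3 days (±1 day at Day 7).

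For each dose: is there a 2-hour check, and if not, days to first look = next scheduled site assessment − dosing day.

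| Injection | Day | Superseded rule | Current rule: first scheduled look |
|---|---|---|---|
| 1 | 0 | 2 hours | 2 hours |
| 2 | 30 | 2 hours | 60 − 30 = 30 days |
| 3 | 60 | 2 hours | 90 − 60 = 30 days |
| 4 | 90 | 2 hours | 120 − 90 = 30 days |
| 5 | 120 | 2 hours | 150 − 120 = 30 days |
| 6 | 150 | 2 hours | 180 − 150 = 30 days |
| 7 | 180 | 2 hours | 187 − 180 = 7 days, or 210 − 180 = 30 days if Days 187 and 195 no longer carry the assessment |

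Results:
- 2-hour checks: 7 of 7 under the superseded rule, 1 of 7 under the current one. Share without: 6/7 = 86%.
- First look about 30 days later: 5/7 = 71%. With ±3 days at both visits the interval runs from 30 − 6 = 24 to 30 + 6 = 36 days.
- If all 156 Phase 2 patients received every dose: 156 × 7 = 1092 injections, of which 156 × 6 = 936 have no 2-hour check.
- If only the baseline predose check had been dropped, which is all that the reason in the Section 5.2 and 5.3 rows covers, the count would still be 7 of 7.

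Effect of the minimum fix in Phase 1b: site checks at the PK draws on Days 30 and 180 add injections 2 and 7, giving 3 of 7 with a same-day look and leaving 4/7 = 57% without one.

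Relation to dose selection: V2.0 Section 4.1.1.3 sets the data cut for the dose-selection review when the last Cohort 3 patient completes Day 44, two weeks after dose 2. In V2.0 Table 1, Day 44 carries adverse-event collection and a targeted examination but no marked site assessment. If both features stand in V3.0, that patient reaches the cut without a scheduled site assessment after the second injection. A check at the Day 30 draws would supply one; the Day 180 check comes after the cut for that patient.

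**The case against.** The strongest objection is that the governing schedule cannot be seen. Section 6.2.7 points to Section 3.4, which is in a part of the document not at hand, as is the current Section 5.3. The Appendix 7 excerpts stop at Day 30 for Table 1 and Day 60 for Table 2. Deletions in that log are marked by strikethrough that was largely lost in text extraction, so the Section 5.3 line may not have been deleted in full. This stands as a limit on the supporting evidence. It does not remove the point, because the timing in Section 6.2.7 is itself current text and is explicit.

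A reader might infer that reactions after later doses go unmeasured. The documents do not support that. Each later predose check looks back at the previous injection, Section 6.2.2.6.2 has observed or reported reactions recorded as adverse events, and special-interest events are reported immediately or within 24 hours of site awareness. A reader might also infer that no reaction could still be visible at 30 days. That depends on an assumed duration, which the protocol does not give.

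A reader might treat the mismatch between the change log and the new text as an error in itself. It is not: the log describes superseded text and shows the new timing openly. The incomplete reasons are only evidence that the effect on later doses may not have been intended.

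Both arms follow the same schedule under blinding, so the planned ascertainment does not differ by arm. That protects the comparison from differential assessment, but it does not recover reactions missed in both arms or make dose 1 comparable with later doses. Finally, timed vital signs, "Vital signs will be assessed on Day 0 at predose and at 1 and 2 hours postdose", do not fill the gap; they were limited to Day 0 in V1.0 and V2.0 too and are not part of this edit.

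**Conclusion.** The point holds in a limited form. Section 6.2.7 schedules a same-day injection-site assessment for 1 of 7 injections, against 7 of 7 under the superseded wording. Short-lived reactions after injections 2 to 7 depend on spontaneous report or recall, and first-dose and repeat-dose incidence are not ascertained alike. The stated reasons (no baseline predose check, the grade restriction, general clarification) do not explain dropping the later postdose checks.

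The 1-of-7 count rests on Section 6.2.7 alone. The 30-day gap for injections 2 to 6 follows from the dosing days, provided the current schedule adds no site assessment between doses; the timing for injection 7 rests on V2.0 visit days. The number of reactions missed cannot be calculated from the document, and the between-arm comparison is not shown to be biased. The Phase 2 primary endpoint, significance level and power are untouched. This is a worthwhile, inexpensive improvement to safety ascertainment, not a flaw that undermines the trial.

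**What to change.** Reconcile Sections 6.2.7, 5.3 and 3.4 with each other and with the stated reason for the edit, so that one timing rule applies throughout.

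At minimum, record an injection-site assessment in Phase 1b at the 4-, 8- and 24-hour PK draws on Days 30 and 180, if footnote p still stands in V3.0. Patients are already seen then, so the cost is a few skin checks and data entries and no extra visit.

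For the other dosing visits, the sponsor should choose openly between two courses. One is to reinstate the postdose assessment carried in V2.0, at the price of a postdose wait at those visits. The other is to keep the current rule and state in the protocol that repeat-dose injection-site incidence rests on predose checks, follow-up visits and reported adverse events, so that results by dose number are read accordingly. The second course costs only wording.
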